Cordeiro et al. recently reported that six-year reconstruction failure rates were higher for irradiated tissue expanders compared to permanent implants, but initial tissue expander placement was associated with a higher proportion of good-to-excellent cosmetic results compared to an initial permanent implant.²⁰

Modification of the conventional radiation schedule may yield improved outcomes:

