5.3 Stratification Factors and Treatment Assignment

400 patients will be randomized 1:1 into either Arm 1 (short-course PMRT) or Arm 2 (long-course PMRT).

Randomization will be stratified by treatment center and age of the patient (<45 vs. ≥45).

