After "Annual Follow up 10 of 10"	➤ Off-study CRF	Site CRP or CSC should: ➤ Submit electronically via InForm
As needed, at any time from baseline through end of 10-year follow up period	➤ Change in Status CRF	Site CRP or CSC should: ➤ Submit electronically via InForm

[^]The "12-months" timepoint (defined as 12-months after initiation of PMRT) and the "Annual Follow up 1 of 10" timepoint (defined as 1-year after initiation of PMRT) overlap, meaning that they both occur on the same date.

Note about missing forms:

- If any of the following forms are missing for a participant, then this would constitute a major protocol violation:
 - Eligibility checklist
 - Baseline Medical Record Review CRF
 - Solicited Adverse Event CRF
 - Cosmetic Outcomes CRF
 - Off Treatment CRF
 - Expedited Serious Adverse Event (SAE) Reporting CRF
 - Follow-up Medical Record Review CRF
 - Change in Status CRF

- The following questionnaires **are required**; however, if any of the following are missing for a participant despite best efforts by Central Study Coordinator and Site Staff to collect from participant, then this does not constitute a major or minor protocol violation:
 - Baseline Patient Questionnaire
 - 6-month Patient Questionnaire
 - 12-month Patient Questionnaire
 - 18-month Patient Questionnaire
 - Reconstruction photographs (at baseline, 6, 12, and 18 months)

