The primary analysis and power: We hypothesize that hypofractionated (short-course) radiation therapy has a higher reconstruction success rate, compared to the conventional fractionation (long-course) radiation at 18-months. We will use Chi-square test for 2x2 table to test this superiority hypothesis. We will also construct a two-sided 95% confidence interval for the difference in the composite outcome of reconstruction success likelihood (defined as no major complications, presence of reconstruction, and good or excellent cosmetic outcome). Recent estimates of reconstruction success after implant reconstruction and conventional radiation reveal a 71% likelihood at the 2-year time period.⁴⁶ “**Table: Effect size and power for superiority tests**” shows the available power with various reconstruction success probabilities for hypofractionation (short-course treatment), given the sample size of 400 patients. Variables that may affect outcomes such as chemotherapy regimen, endocrine therapy and patient age will be assessed for impact to ensure balance between both treatment arms.

Table: Effect size and power for superiority tests		
Reconstruction Success Likelihood (%)		Power (%)
Long-course radiation	Short-course radiation	
71.0	82.8	80
71.0	84.4	90

N=400 randomized patients and α (two-sided)=0.05

[figure not shown]
Data monitoring of local/regional recurrence event:

We will also follow oncologic outcomes to exclude any unexpected increase in the risk of recurrence with hypofractionation (short-course) radiation therapy, although a detectable increase in recurrence rates is unlikely given data from prior experiences of hypofractionation. The cumulative incidence of local or regional recurrence in a recent series of post-mastectomy

radiation therapy is about 2% at 18 months.³ Therefore, in the case where the recurrence rate is suggested to be statistically significantly greater than 2%, the study will be suspended to allow for investigation.

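### Section 10c tests 18-month reconstruction success without the pre-radiation cosmetic rating the trial already collects, so precision may be forgone

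*Combined protocol and SAP*

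**What the plan says.** The hypothesis in 10c is that the short course "has a higher reconstruction success rate, compared to the conventional fractionation (long-course) radiation at 18-months". Success is a composite, "defined as no major complications, presence of reconstruction, and good or excellent cosmetic outcome". The method is given in one sentence, "We will use Chi-square test for 2x2 table to test this superiority hypothesis", with a 95% confidence interval for the difference. The power table gives 80% for 71.0% against 82.8% and 90% for 71.0% against 84.4%, with "N=400 randomized patients and α (two-sided)=0.05".

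Other variables enter 10c in one sentence only. Chemotherapy regimen, endocrine therapy and age are offered as examples of factors that "will be assessed for impact to ensure balance between both treatment arms".

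Section 9.1 lists "Reconstruction photographs (at baseline, 6, 12, and 18 months", and its table has a study chair or delegate complete a Cosmetic Outcomes CRF at each of those times. The baseline one precedes radiation. That rating is absent from the composite and its test, from the stratification factors in 5.3 (center and age group), from the examples in the balance sentence, and from the subgroup table in 10e.

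Section 10b treats the primary endpoint differently: the FACT-B physical well-being score is analysed as change from its pre-radiation value, expressly to account for baseline, with age group in the model.

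**The concern.** Cosmesis is one of three components of the composite, so the unused variable is the baseline value of part of the endpoint. Such a variable is a natural candidate for a prognostic covariate, and this one is already planned for the database. The plan accepts the principle for physical well-being and gives no reason for doing otherwise in 10c.

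The balance sentence does not fill the gap. Looking at covariates cannot produce balance, the list is open-ended, and no consequence follows from what is found. It adds no precision and does not say whether an adjusted result will be reported or which one.

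At stake is the power of the main clinical comparison, planned at 80% for a gain of 82.8 − 71.0 = 11.8 points.

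**Working it through.** **Inputs from the plan.** 200 per arm (5.3: "400 patients will be randomized 1:1 into either Arm 1 (short-course PMRT) or Arm 2 (long-course PMRT"), two-sided alpha 0.05, long-course success 0.71, short-course success 0.828 or 0.844 (10c).

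**Step 1: reproduce the stated power.** For a two-proportion test with p̄ the mean of the two rates:

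power = Φ{ [d − 1.96·√(2p̄(1−p̄)/200)] / √[(p₁(1−p₁)+p₂(1−p₂))/200] }

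- 0.71 v 0.828: d = 0.118, p̄ = 0.769. Null SE = √(2×0.769×0.231/200) = 0.04215. Alternative SE = √[(0.2059+0.1424)/200] = 0.04173. Power = Φ[(0.118 − 0.0826)/0.04173] = Φ(0.848) = 80.2%.
- 0.71 v 0.844: d = 0.134, p̄ = 0.777, SEs 0.04163 and 0.04108. Power = Φ(1.276) = 89.9%.

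Both rows of the table are right.

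**Step 2: add the baseline rating.** Two quantities are needed that the documents do not give, so both are assumed: q, the share rated below good before radiation, and s, the 18-month success rate of those women on long course. Overall rates stay at 71% and 82.8%, so the plan's effect is unchanged. Then:

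- long-course success in the other women: g = (0.71 − q·s)/(1 − q);
- a common odds ratio ψ, with f(p) = ψp/(1−p+ψp), solves (1−q)f(g) + q·f(s) = 0.828;
- null variance of the stratified difference = (2/200)[(1−q)ḡ(1−ḡ) + q·s̄(1−s̄)], where ḡ and s̄ are the two-arm means within each stratum. The alternative variance uses the arm-specific rates in the same way.

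Worked case, q = 20%, s = 30%:
- g = (0.71 − 0.06)/0.80 = 0.8125. ψ = 2.333 gives f(g) = 0.910 and f(s) = 0.500. Check: 0.8×0.910 + 0.2×0.500 = 0.828.
- ḡ = 0.861, s̄ = 0.400. Null variance = 0.01×[0.0956 + 0.0480] = 0.001436, SE 0.03790 (unstratified 0.04215).
- Alternative variance = [0.8(0.0819+0.1523) + 0.2(0.2500+0.2100)]/200 = 0.001397, SE 0.03738.
- Power = Φ[(0.118 − 0.0743)/0.03738] = Φ(1.170) = 87.9%.

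**Step 3: the range.** Formula as above; simulation is a Mantel-Haenszel test stratified on baseline rating (20,000 to 100,000 trials per row). The raw chi-square has about 80% to 81% power in every row.

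| q | s | Formula | Simulation |
|---|---|---|---|
| 15% | 40% | 83.3% | 83.5% |
| 15% | 30% | 85.8% | 86.2% |
| 20% | 40% | 84.5% | 84.7% |
| 20% | 30% | 87.9% | 88.3% |
| 30% | 40% | 87.2% | 87.4% |
| 30% | 30% | 92.1% | 92.3% |
| 20% | 50% | 82.1% | 82.3% |
| 20% | 71% (not prognostic) | 80.2% | 80.1% |

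**Step 4: does it carry over to a standardised risk difference?** In simulation, the risk difference standardised over the baseline rating had 88.6% power at q = 20%, s = 30% (Mantel-Haenszel 88.3%), and 82.8% at q = 20%, s = 50% (82.3%).

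**Step 5: restricting to women good or better at baseline.** With overall rates held as above and s from 25% to 71%, power in that subset is 56% to 80% over q = 5% to 30%. It is no substitute for the adjusted analysis.

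**The case against.** The strongest case against is that nothing in 10c is wrong. Randomisation makes the chi-square test valid and free of bias, absolute success at 18 months is a legitimate endpoint, and the planned power is correct. All of that stands.

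The baseline rating may also predict poorly. Section 1.1 describes expanders as temporary devices later exchanged for an implant, and 5.2 allows inflation to continue after randomisation, so the early photograph may show an unfinished reconstruction. That is a fair reason to take the lower rows of the table seriously. It does not argue against adjusting, because the cost in the non-prognostic row is negligible.

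Missing baseline ratings would reduce the gain. Section 9.1 does not count missing photographs as a violation, although a missing Cosmetic Outcomes CRF is a major one. This stands too, and the fix must provide for it.

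Four stronger readings are tempting and not supported:

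- *Women with a low baseline rating count as failures.* The definition looks only at 18 months. Such a woman succeeds if she is then good or excellent and meets the other two components. If all such women failed in both arms, they could be at most 1 − 0.828 = 17.2% of patients, or the plan's short-course rate could not be reached.
- *The planned power is overstated.* It is calculated from overall success rates and needs no deduction for low baseline ratings, provided the 71% comes from a comparable unselected population.
- *The balance check allows the test to be changed.* The text names one test and does not say that the check can alter it. The check is open-ended, no more.
- *Omitting expander versus implant is a comparable gap.* Section 1.1 reports that "six-year reconstruction failure rates were higher for irradiated tissue expanders compared to permanent implants", but also that starting with an expander gave more good-to-excellent cosmetic results. In a composite holding both, these may offset, and 10e already lists the factor for subgroup analysis.

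**Conclusion.** The point holds as one of efficiency and prespecification, not of validity. A baseline measure of one component of the composite is collected and then left unused, while an open-ended balance check stands where an adjusted analysis should be.

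Under the assumed 15% to 30% below good and 30% to 40% long-course success among them, power rises from about 80% to between about 83.5% and 92%. It rises by about 2 points at 20% and 50%, and not at all if the rating is not prognostic. These figures assume a common odds ratio, overall rates of 71% and 82.8%, and a complete baseline rating in two categories. The visible text does not name the categories below good. The scale may be on pages not available for review, so that is not counted as a fault.

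The change should be made because it is nearly free. The trial's primary endpoint, physical well-being at 6 months, is not affected.

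**What to change.** In 10c, before any comparison by arm is run:

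1. Keep the composite as defined.
2. Replace the balance sentence with one prespecified analysis: a logistic regression on arm, baseline cosmetic rating (good or excellent versus lower) and age group (<45, ≥45), reported as a standardised risk difference with 95% confidence interval. This keeps the difference in success rates as the quantity estimated. Age group is a stratification factor and is already in the 10b model.
3. Give missing baseline ratings their own category. Because 9.1 places the baseline photographs after enrollment, and so possibly after allocation, have them rated without sight of the arm.
4. State in advance that the adjusted analysis is the main comparison, and report the raw 2x2 chi-square beside it.
5. Treat expander versus implant as an optional further covariate, decided now, and results in women good or excellent at baseline as descriptive only.

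The cost is SAP wording and one extra model. No new data and no change in sample size are needed.

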- **CLINICIAN WITHDRAWAL:** Clinician took participant off protocol treatment (PMRT). Please note that after taking a subject off protocol treatment, study questionnaires and follow-up CONTINUE through the 10-year follow up period. Site study staff should complete all Medical Record Abstraction CRFs and Follow-up CRFs.
- **DEATH:** If a study participant dies, the site staff should complete all Medical Record Abstraction CRFs through death. After all data has been collected through death, sites may take participant off study by submitting the Off-Study CRF via InForm.
- **FOUND TO BE INELIGIBLE:** Participant was enrolled on the trial but was later found to be ineligible. Select one:
 - a. Yes, protocol treatment (PMRT) will continue [treating physician and study chairs agree there are no safety concerns if the patient continues protocol treatment].
 - b. No, protocol treatment will not continue [in this case, study questionnaires and follow up should continue through the 10 year follow up period. Site study staff should complete all Medical Record Abstraction CRFs no matter how long the subject actually received protocol treatment].
- **SWITCHED ARMS:** If inhomogeneity constraints are not attainable in the hypofractionated setting, the patient will be treated with standard fractionation as per protocol. Switching arms in this case is permitted, and these participants who switch arms will still be asked to complete all patient questionnaires and will be followed for 10 years
- **OTHER:** Please specify.
 - **Note:** If a participant experiences a distant recurrence, they should be withdrawn from the study by selecting this option in InForm. Once participants are withdrawn from the study due to distant recurrence, all follow-up should be discontinued.

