10. STATISTICAL CONSIDERATIONS

10a. Accrual: Based on previous years' treatment records, we anticipate that there will be about 40-50 eligible patients per month across the multiple participating academic and community centers. The accrual rate of this study is expected to be about 22 patients per month. We expect conservatively (based on survey data) that 75% of the eligible patients (after confirmation of the need for radiation therapy) are willing to be randomized to either the long-course or short-course treatment. The accrual will be open until 400 patients are enrolled. Randomization will be stratified by treatment center and age of the patient (<45 vs. ≥45). We expect the proportion of patients in the younger cohort of the study sample to be 40%. The anticipated length of the accrual period is 21-27 months.

10b. Statistical analysis plan for patient-reported quality of life outcomes and power considerations

Quality of life (QoL) measurement and the primary endpoint: We will use an array of instruments to rigorously assess quality of life among study participants, such as the FACT-B scores, satisfaction with breast surgery outcomes (BREAST-Q), Lymph-ICF, and financial burden. We will record and report all reasons for dropout and which outcomes were not reported, and include this data in our final reports. FACT-B (version 4) specifically measures quality of life in breast cancer patients and includes modules for assessing physical well-being, emotional well-being, social well-being, functional well-being and a 2-item question characterizing a breast cancer patient's relationship with her physician. QoL will be assessed at baseline, 6 months, 12

months and 18 months. This data will allow peer reviewers and readers of our publications to assess the validity of our study.

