Under the same setting as shown described above, “**Table: N=400 randomized patients, $\alpha=0.05$** ” reveals the power to detect an age interaction will be 59%-89%. These are conservative estimates for the 6-month change in PWB, given that patients in our survey were interviewed between 6 and 24 months (data not shown, manuscript in preparation), and there may be some recovery in physical symptoms with time.

Table: N=400 randomized patients, $\alpha=0.05$.				
PWB score Δ		SD of Δ	Power	
Younger patients	Older patients		Main analysis	Interaction
4.0	2.0	3.5	>0.99	0.80
4.0	2.0	4.0	>0.99	0.69
4.0	2.0	4.5	>0.99	0.59

Strategy for handling missing data: Given the patient incentives, short time required to complete surveys, and enthusiasm voiced by the patients we surveyed, we expect that the dropout fraction from the study at 6 months will be at most 5% and that the dropout mechanism would be mostly random. In a primary analysis, we will exclude those who dropout from the study or who do not have data at 6 months. However, because a random missing mechanism assumption is not verifiable empirically, we will use several methods to handle missing observations to confirm the stability of the findings from the primary analysis. Specifically, we will perform the following: (1) last observation carried forward (LOCF), (2) mean value imputation, (3) worst-case and (4) best-case imputation. We will also conduct (5) multiple imputation⁵¹. For multiple imputation, we will create 10 complete datasets, imputing the missing values using chained equations. We will perform the analysis with the 10 complete datasets and integrate the results with Rubin’s method of imputation.⁵¹ For another approach, we will analyze this data according to (6) the methods described in Schluchter and in Schluchter, Greene and Beck.^{52,53} These methods take into account the possibility of informative “missingness” by jointly modeling the longitudinal responses (here, QoL scores) and the time to dropout.

Other QoL analysis: In secondary analyses, we will use generalized estimating equation (i.e., marginal modeling) and random-effects models to analyze longitudinal data⁵⁴ (i.e., baseline, 6 months, 12 months and 18 months) for the FACT-B total score (37 items) and each subscale as well as the primary endpoint (FACT-B PWB subscale).

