We hypothesize that patients randomized to short-course radiation will have increased satisfaction with their reconstruction as measured by the BREAST-Q reconstruction survey. We

will use a two-sample t-test for the BREAST-Q satisfaction score, and a chi-square test for 2x2 tables for post-decision regret. We consider a difference of 10 points in the BREAST-Q satisfaction score to be clinically meaningful. With the given total sample size of 400 (200 per arm), we will be able to detect this difference with 80% or higher power at a two-sided 0.05 significance level, if the standard deviation of the score is equal to or smaller than 35.6.

Strategy for handling missing data in other QoL analysis: To assess the robustness of our results, we will perform several sensitivity analyses as well as complete case analysis. For example, we will perform worst-case or best-case imputation or generalized linear modeling in combination with multiple imputation⁵¹ methodology.

Patient-centered outcomes analysis: Furthermore, we will also consider a new outcome that integrates tailored patient-prioritized quality of life measurement. As seen in our patient survey, the relative importance of QoL domains vary from patient to patient. At the baseline visit, we will ask each patient to give a weight to each FACT-B subscale based on its importance for her. We will then calculate a “weighted” total score of FACT-B (37 items) for each individual, using these weights. The weights will be standardized for each patient, so that the range of the weighted score can match with that of the FACT-B total score. We will perform the same analyses described above to assess the impact of the intervention on this exploratory new outcome that may enhance the measurement of patient-centered outcomes.

10c. Statistical analysis plan for clinical and oncologic outcomes and power consideration

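### The reconstruction-success power table and the BREAST-Q SD limit count all 400 randomised patients as evaluable, so both are slightly optimistic once any loss occurs

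*Combined protocol and SAP*

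**What the plan says.** **Sample size.** Section 5.3 says "400 patients will be randomized 1:1 into either Arm 1 (short-course PMRT) or Arm 2 (long-course PMRT"), and section 10a says "The accrual will be open until 400 patients are enrolled". Neither adds patients to cover loss.

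**Reconstruction success (section 10c).** A chi-square test compares the arms at 18 months on a composite: free of major complications, reconstruction still in place, and a cosmetic result rated good or excellent. Against 71.0% in the long-course arm, the table gives 80% power for 82.8% and 90% power for 84.4%. It is described as holding "given the sample size of 400 patients" and is labelled "N=400 randomized patients and α (two-sided)=0.05".

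**BREAST-Q (section 10b, Other QoL analysis).** A two-sample t-test is to detect 10 points with at least 80% power if the SD is no more than 35.6. The basis is "With the given total sample size of 400 (200 per arm").

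**Loss.** The missing-data paragraph for the primary endpoint says "we expect that the dropout fraction from the study at 6 months will be at most 5" percent. This is the only loss rate in the documents. Section 8 says of distant recurrence: "Once participants are withdrawn from the study due to distant recurrence, all follow-up should be discontinued". Section 9.1 says of questionnaires and photographs that stay missing despite best efforts: "then this does not constitute a major or minor protocol violation". The same note makes a missing Cosmetic Outcomes CRF a major violation, and section 8 gives a fallback for completing that form when photographs cannot be submitted. No loss rate is given for 18 months, and no missing-data rule is given for the composite.

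**The concern.** A power statement labelled by patients randomised should allow for patients who will not contribute an outcome. Here the number randomised and the number analysed are taken to be equal, while other parts of the plan provide for loss. The 80% row has no slack: it needs 200 evaluable patients per arm, and exactly 200 are randomised. The reconstruction endpoint is read a year after the time point to which the 5% applies. Follow-up also ends at distant recurrence in a population that extends to stage III. What is at stake is how well the stated power describes two secondary comparisons, and how a null result on them would be read.

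**Working it through.** **Inputs.** 71.0% against 82.8% or 84.4%, two-sided alpha 0.05, 400 randomised 1:1 (sections 5.3 and 10c). BREAST-Q difference of 10 points and SD limit of 35.6 (section 10b). Loss of 5% is the 6-month figure from section 10b carried forward to 18 months. Loss of 10% is an assumption. Evaluable patients per arm: 200 × 0.95 = 190 and 200 × 0.90 = 180.

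**Reconstruction success.** Pooled-variance chi-square power, with p̄ the mean of the two rates and q = 1 − p:

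power = Φ{ [d − 1.96 √(2p̄q̄/n)] / √[(p1q1 + p2q2)/n] }

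For 71.0% against 82.8%: d = 0.118, p̄ = 0.769, 2p̄q̄ = 0.3553, p1q1 + p2q2 = 0.2059 + 0.1424 = 0.3483.

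- n = 200: (0.118 − 0.0826)/0.0417 = 0.848, power 80.2%. This reproduces the stated 80%.
- n = 190: (0.118 − 0.0848)/0.0428 = 0.777, power 78.1%.
- n = 180: (0.118 − 0.0871)/0.0440 = 0.703, power 75.9%.

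For 71.0% against 84.4%: d = 0.134, p̄ = 0.777, 2p̄q̄ = 0.3465, p1q1 + p2q2 = 0.2059 + 0.1317 = 0.3376.

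- n = 200: (0.134 − 0.0816)/0.0411 = 1.276, power 89.9%. This reproduces the stated 90%.
- n = 190: (0.134 − 0.0837)/0.0422 = 1.193, power 88.4%.
- n = 180: (0.134 − 0.0860)/0.0433 = 1.108, power 86.6%.

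Solving the same formula for the short-course rate gives the detectable rates in the table below.

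**BREAST-Q.** With a normal approximation, the SD limit is 10 / [(1.960 + 0.842) √(2/n)], which is 35.7 at n = 200. The noncentral t gives 35.6, the stated figure. The limit scales with √n: 35.6 × √0.95 = 34.7 and 35.6 × √0.90 = 33.8.

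| Evaluable (total) | Power, 71.0 v 82.8 | Power, 71.0 v 84.4 | Rate detectable at 80% / 90% power | BREAST-Q SD limit |
|---|---|---|---|---|
| 400 (no loss) | 80.2% | 89.9% | 82.8% / 84.4% | 35.6 |
| 380 (5%) | 78.1% | 88.4% | 83.1% / 84.7% | 34.7 |
| 360 (10%, assumed) | 75.9% | 86.6% | 83.4% / 85.1% | 33.8 |

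**Primary endpoint.** For a difference of 2.8 and an SD of 4.0 (section 10b), even 20% loss (160 per arm) gives 2.8 / [4.0 √(2/160)] = 6.26. Then 6.26 − 1.96 = 4.30, so power is above 99%.

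**The case against.** The sponsor could fairly say four things.

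- **The arithmetic is right and the condition is stated.** Both statements name 400. A reader might infer that the calculations are wrong or that the design cannot deliver its stated power. The documents do not support that: every figure reproduces at 200 per arm. What remains is the label, since the table speaks of patients randomised and the calculation needs patients evaluable.
- **The 5% belongs to another endpoint.** It is an upper limit for the 6-month questionnaire, justified by incentives and short surveys. The composite draws on charts and photographs, and chart abstraction continues after most withdrawals. This stands. Using 5% at 18 months is an assumption, no distant-recurrence rate is given, and nothing in the documents shows that evaluable numbers will fall below 380.
- **The effect is small.** The fall is 1.5 to 2 points of power at 5% loss, and the detectable rate moves by 0.3 points. The 71% control rate is itself a 2-year estimate. This stands and sets the weight of the point.
- **Missing photographs are provided for.** A reader might infer that patients without photographs will be dropped, so that chart-known failures are kept while successes are lost. The plan states no such rule for the composite. It makes a missing Cosmetic Outcomes CRF a major violation and gives a fallback for completing the form. Any size put on such a bias would need a missing-photograph rate and a share of chart-detected failures, and the documents give neither. The plan's gap here is silence on how a rating that is still missing would be analysed.

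**Conclusion.** The point holds as a minor correction. The power table and the SD limit are correct for 400 evaluable patients and slightly optimistic for 400 randomised. At 5% loss, power is about 78% and 88%. At 10% it is about 76% and 87%, but that rests wholly on an assumed loss. Both results assume equal loss in the two arms, unrelated to outcome.

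For BREAST-Q, only the SD limit moves. A reader might infer that its power falls below 80%. That cannot be shown, because section 10b gives neither an expected SD nor a time point for the test. If the true SD is 34.7 or less, power stays at 80% or more with 380 evaluable patients.

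The effect is confined to these secondary outcomes and does not reach the Physical Well-Being primary endpoint.

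**What to change.** In section 10c, restate the power table on evaluable patients: 78% and 88% at 380, with 76% and 87% at 360 labelled as an assumed 10% loss. Give the matching detectable rates (83.1%/84.7% and 83.4%/85.1%). In section 10b, give the BREAST-Q SD limit as 34.7 at 380 and 33.8 at 360. Say that the 5% is the 6-month figure carried forward.

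As an optional addition, state in section 10c that failures known from the chart count for every patient, and that a cosmetic rating still missing after the section 8 fallback is multiply imputed by the method already planned for quality of life.

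The cost is a few changed numbers, slightly less favourable stated power and, if the option is taken, one more use of a planned method. No further enrolment is proposed. For comparison, holding 80% and 90% power at 5% loss would take 200/0.95 = 211 and 201/0.95 = 212 per arm after rounding up (422 to 424 in total), which a 2-point shortfall on a secondary outcome does not justify.
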